We will use the cut-points established by Trost and colleagues:  $\leq 48$  cp15s for sedentary behaviour (SED), 49-418 cp15s for light physical activity (LPA), and  $>418$  cp15s for moderate-to-vigorous physical activity (MVPA) . These cut-points were chosen because they were derived from direct observation of a sample of toddler and preschool-aged children while wearing the ActiGraph GT1M accelerometer . Videos of the children playing were coded using a modified version of the Children's Activity Rating Scale before receiver operating characteristic curve analyses were conducted to determine the corresponding cut-points to the 3 categories of interest: SED, LPA, and MVPA . These results were found to exhibit excellent classification accuracy . They were then cross-validated against pre-existing cut-points that are established for toddlers and preschoolers, which were not found to be significantly different than the pre-established cut points established by Pate and colleagues  and those established by National Health and Nutrition Examination Survey .

We will then be able to calculate total time (minutes) as well as proportion of time (%) spent in each activity category (SED, LPA, MVPA). The overall mean cp15s for each child will be based on all 15-second epochs that occurred during eligible wear periods from the time that the caregiver indicated the child woke up until the time that the caregiver indicated the child went to sleep at. If this data is missing, we will use eligible wear periods between 8am to 8pm. This mean will exclude non-wear periods as defined above and when the accelerometer was not being worn by the child (based on daily logs collected from the caregivers via afternoon telephone call; Section 9.3.7.).

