For each child, we will calculate the mean number of minutes per day and the proportions of the child's total eligible wear time that are classified as SED, LPA and MVPA. We will also determine the proportion of days on which each child reached or exceeded 180 minutes of activity classified as LPA or MVPA, and the proportion of days on which each child reached or exceeded 60 minutes of activity classified as MVPA. These cut-offs are based on the Canadian preschooler physical activity guidelines established by Tremblay and colleagues , as there are no Bangladeshi standards available at present. If Bangladeshi guidelines are released before data analysis and reporting is completed, we will also apply those standards in our analyses.

For each child, we will establish the following parameters related to accelerometry:

- Total duration (minutes) of the potential data collection period on all days on which the accelerometer was instructed to be worn;
- Total eligible wear time (minutes), including data collected while the child was awake (from the time that their caregiver indicated that they woke up until the time that they went to sleep). If this data is not provided, total eligible wear time will be measured between 8am and 8pm. Non-wear periods will be excluded based on the following

criteria:  $\geq 20$  minutes of 0 cp15s allowing for up to 2 minutes of 0-100 cp15s in that period. A given day will be considered eligible for inclusion if there are at least 10 hours/day (600 min) between the indicated time period that the child was awake at, or between 8am to 8pm of wear time for those with missing data, after excluding non-wear periods;

- Total indoor eligible wear time (minutes; excluding non-wear periods as previously defined), based on maternal report;
- Total eligible wear time in or around the home (minutes; excluding non-wear periods as previously defined), based on combination of maternal report and GPS logging. "Around the home" will be defined as occurring in the same building or property of the home (e.g., rooftop, neighbouring apartment in the same building, common areas of the apartment building, private courtyard areas that are on the same property as the home in which the child resides).

For purposes of secondary and sensitivity analyses, we will also estimate for each child:

- Mean cp15s for indoor activity
- Mean cp15s for activity in or around the home

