- Mean cp15s on a day that is typically a work day (Sunday through Thursday)
- Mean cp15s on a Friday and/or Saturday (weekend)

For each of the above measures, we will also classify the activity in terms of average daily minutes and proportion of total time spent in SED state, LPA state, and MVPA state. In sensitivity analyses, we will compare the average daily minutes and proportion of total time spent in each activity category across different cut-off points that have been established by various research groups:

- Proportion of time spent in activity categories established by Pate and colleagues (SED:  $\leq 199$  cp15s; LPA: 200-419 cp15s; MVPA  $\geq 420$  cp15s)
- Proportion of time spent in activity categories established by Sirard and colleagues (SED:  $\leq 301$  cp15s; LPA: 302-614 cp15s; MVPA  $\geq 615$  cp15s) Proportion of time spent in activity categories established by Van Cauwenberge and colleagues (SED:  $\leq 372$  cp15s; LPA: 373-584 cp15s; MVPA  $\geq 585$  cp15s)

To address aim 4, we will analyze sleep quality and quantity directly on the nighttime accelerometry wear periods. Sleep data will be measured in 60-second epochs. This is obtained from the same accelerometry file that the activity data is derived from; however, data will be re-integrated into a 60-second epoch file (analyzes number of activity counts in every 60-second period).

Using the manufacturer's add-on to the ActiLife software (ActiLife 6 Full sleep Features Upgrade), we will be able to detect the number of sleep periods as well as the duration and quality of the sleep periods within the accelerometry file for each participant. The software will also detect and describe:

- Time in bed/out of bed (am/pm); duration in bed (hours; min)
- Sleep onset (when sleep commenced; am/pm)
- Total Sleep Time (TST; hours, min)
- Wake After Sleep Onset (WASO; describes how many minutes after sleep onset the participant woke up; min)
- Awakenings (number of awakenings during sleep onset)
- Average awakenings (average duration of awakenings during sleep onset; min)
- Total activity counts during sleep period (cp60s)
- Movement Index (MI)
- Fragmentation Index (FI)
- Sleep Fragmentation Index (SFI)
- Sleep Efficiency (%)

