To address our first objective, we will first create a histogram of the distribution of the data to assess the spread and shape of the frequency distribution of each of the categories of all of the physical activity data (average cp15s across all days for each participant). The number of bins within the histogram will be determined using the equation  $1 + 3.3\log_{10}(n)$ . A boxplot will then be created to assess the spread, as measured by the median; interquartile range (IQR); range of observations; presence of outliers; and provide additional information about the shape of the data. Finally, a Q-Q plot will be created to compare the frequency distribution of the data to a normal distribution. Using the shape and direction of the curvature, we will assess any deviation from normality.

We will estimate the mean and 95% confidence interval of cp15s for total physical activity of the sample of children, overall and stratified into the following groups:

- Boys and girls
- BMI categories (underweight, normal, overweight and obese)
- Household food security status (food secure, moderately food insecure; severely food insecure)
- Anemic and non-anemic

We will then summarize the distributions of the average amount (# of minutes) and proportions of wear time spent engaging in SED, LPA, and MVPA, over the measurement period.

Distributions of each time spent in each level of activity will be shown graphically (histograms, kernel density plots) and summarized using conventional descriptive statistics: mean and standard deviation if normally distributed, or median and interquartile range if not normally distributed.

We will then estimate the frequency of children who met Canadian physical activity recommendations on any day, and the average number of days on which children met the recommendations (180 minutes of activity classified as LPA or MVPA, working towards 60 minutes of activity classified as MVPA). Bangladeshi recommended guidelines for preschool-aged children will be used if they are released before statistical analyses begin. These data will be compared to published results in similar international, preschooler populations.

The above analyses will be repeated using data restricted to indoor wear time, in and around the household wear time, on weekdays, and on weekends.

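### Attainment of the 180-minute activity criterion turns on a sedentary/light limit that is 4 to 8 times higher in the plan's alternative cut-point sets, yet attainment is left out of the cut-point sensitivity analysis

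*Combined protocol and SAP*

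**What the plan says.** Section 10.1 gives one main cut-point set: sedentary up to 48 counts per 15 s (cp15s), light (LPA) 49-418, moderate-to-vigorous (MVPA) above 418. Each day is scored on whether the child "reached or exceeded 180 minutes of activity classified as LPA or MVPA" and, separately, on whether the child "reached or exceeded 60 minutes of activity classified as MVPA".

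Section 10.4.1, Objective #1, then reports attainment: "We will then estimate the frequency of children who met Canadian physical activity recommendations on any day", together with the average number of days on which they were met. The criterion is written as "180 minutes of activity classified as LPA or MVPA, working towards 60 minutes of activity classified as MVPA". Of the results, the plan says: "These data will be compared to published results in similar international, preschooler populations". The Objective #1 analyses are repeated for indoor time, time in and around the home, weekdays and weekends. They are not repeated by cut-point set.

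Section 10.1 lists three alternative sets for sensitivity analysis:

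- sedentary up to 199, MVPA from 420;
- sedentary up to 301, MVPA from 615;
- sedentary up to 372, MVPA from 585.

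The stated scope is that "we will compare the average daily minutes and proportion of total time spent in each activity category across different cut-off points". Section 10.4.2 adds a comparison of mean cp15s across the four sets, with an ANOVA. Neither section mentions guideline attainment.

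**The concern.** Attainment is a threshold result built on a classification, and the plan itself treats that classification as uncertain enough to test with three other sets. The 180-minute criterion uses only the boundary on which the sets disagree most. As planned, the reader gets one attainment figure from the set with by far the lowest sedentary limit, and nothing shows how many children or days would change status under the others.

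The comparison with published results raises the stakes. The plan does not require the comparator to have used the same cut-points. A difference in attainment between this sample and another could therefore come from the limits alone and be read as a difference between children.

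The section 10.4.2 comparison does not fill the gap. Mean cp15s averages all eligible epochs before any classification, so as worded it is the same number under every set.

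**Working it through.** **The plan's own figure.** Section 9.6 gives a margin of ±2.45 cp15s: 1.96 × 9.7 / √60 = 2.45. It reproduces. It concerns mean cp15s and is untouched by this point.

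**Which boundary matters.** Active minutes = LPA + MVPA = wear time × P(count > sedentary limit). The LPA/MVPA boundary cancels.

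- Sedentary limits against the main set: 199/48 = 4.1; 301/48 = 6.3; 372/48 = 7.8.
- MVPA lower bounds against the main set: 420/419 = 1.00; 615/419 = 1.47; 585/419 = 1.40.

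**Illustration.** The documents give no epoch distribution, so these inputs are assumptions:

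- share sedentary under the main set, s = 45%, 55% or 65%;
- share MVPA under the main set, m = 5%, 8% or 10%;
- three shapes fitted exactly to s and m: log-normal, Weibull, and exponential with excess zeros.

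That makes 27 scenarios at each wear time. Wear times are 600 min (the eligibility minimum in section 10.1), 720 min (the whole 8am-8pm fallback window) and 870 min (an assumed longer waking day).

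*Log-normal example, s = 55%, m = 8%, 720 min.* σ = (ln 418 − ln 48)/(1.4051 − 0.1257) = 2.1643/1.2794 = 1.692. μ = 3.8712 − 1.692 × 0.1257 = 3.659. Shares above 48, 199, 301 and 372 are 0.450, 0.167, 0.113 and 0.091, giving 324, 120, 81 and 65 min.

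*Excess-zeros example, s = 45%, m = 10%, 720 min.* P(count > c) = 0.55 × exp(−r(c − 48)), with r = ln(0.55/0.10)/370 = 0.00461. Shares above 199, 301 and 372 are 0.274, 0.171 and 0.124, giving 197, 123 and 89 min.

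Lowest and highest active minutes over the 27 scenarios (the 600 and 870 rows are the 720 row times 600/720 and 870/720, before rounding):

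| Wear | limit 48 | limit 199 | limit 301 | limit 372 |
|---|---|---|---|---|
| 600 min | 210-330 | 68-165 | 44-103 | 34-74 |
| 720 min | 252-396 | 81-197 | 53-123 | 41-89 |
| 870 min | 305-479 | 98-239 | 64-149 | 50-108 |

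All 81 days meet 180 min at limit 48. None does at 301 or 372. At 199, the number meeting it is 0 of 27 at 600 min, 2 of 27 at 720 min and 8 of 27 at 870 min.

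**Different assumptions.** I also set mean counts of 100-200 cp15s directly, with exponential, log-normal (σ = 1.5) or 40%-zeros-plus-exponential shapes and 600-720 worn minutes. Active minutes were 238-566, 68-266, 30-175 and 15-142 for the four limits, which is the same pattern. The 175 comes from a very active day, with 123 min MVPA in 720 (17%). Over 870 min it would be 175 × 870/720 = 211, so a sufficiently active child passes even at 301.

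**The 60-minute criterion.** At 720 min, m = 5%-10% gives 36-72 min of MVPA under the main set. The 199 set is almost identical because its MVPA limit is 420. Under the sets with MVPA limits of 585 and 615, the log-normal and Weibull scenarios give 13-56 min. A child at 72 min would lose this criterion too.

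**The case against.** The strongest reply is that section 10.1 already plans average daily minutes and proportions under all four sets. A table with mean active time well above 180 min in one column and below it in others would reveal the dependence. That stands in part, so a reader who infers that the report would hide the issue goes too far. But mean minutes do not give the number of children or days crossing a threshold, which is what section 10.4.1 reports.

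A pre-specified main set is legitimate, and nothing here argues against it. Section 10.4.1 does not restate which set it uses for attainment; that it is the main one is inferred from section 10.1.

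A reader might infer that a child who meets 180 min under the main set fails under all three others. The working does not support that: the 199 set can pass, most often on long days. The illustration also scores a single day. The any-day rule in section 10.4.1 is easier to meet over several days, so the table cannot say how many children would be reclassified.

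A reader might also infer that the validation statement in section 10.1 ("They were then cross-validated against pre-existing cut-points that are established for toddlers and preschoolers") is wrong, because the sedentary limits are 48 and 199 while the MVPA limits nearly agree. The documents do not support this. The sentence reports a cited study's finding and does not say which limits were tested or how.

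Finally, section 10.4.1 names no comparator and does not say that cut-points will be ignored. Excluding every study with other cut-points would be stricter than necessary.

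**Conclusion.** The point holds as a minor improvement. It is certain from the text that the 180-minute criterion uses only the sedentary/light limit among the cut-points, that this limit is 4.1 to 7.8 times higher in the alternative sets, and that no section re-estimates attainment under them. The size of the effect rests on assumed epoch distributions. Within 45%-65% sedentary, 5%-10% MVPA and 600-870 worn minutes, the day's status reverses in every scenario for the 301 and 372 sets, and in 71 of 81 for the 199 set (81 − 10). Far more active days could pass under more sets.

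It should not be read as a threat to the study's main result. The primary measure in section 10.1, the sample size in section 9.6 and the models for Objectives 2 and 3 all use mean cp15s, which no cut-point changes. Attainment is one descriptive output of Objective 1.

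**What to change.** 1. In sections 10.1 and 10.4.2, re-estimate under all four sets the attainment measures already defined: children meeting the recommendations on any day, average number of days met, and proportion of days with at least 180 min LPA or MVPA and with at least 60 min MVPA. Report the four values side by side, with the main set as primary.
2. In section 10.4.1, compare each published attainment figure with this study's estimate under the same cut-points where available. Otherwise state the comparator's cut-points and draw no conclusion about the difference.
3. In section 10.4.2, replace the comparison of mean cp15s across cut-point sets with this comparison of category time and attainment.

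The validation statement in section 10.1 can stay as it is. The cost is a few lines of code and one table, on data that section 10.1 already has classified under all four sets. No new data are needed. The downside is that attainment appears as a range.

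### Guideline attainment (180 active minutes, 60 MVPA minutes per day) should not be repeated on indoor-only and home-only wear time, where a whole-day target can only be met as often or less often

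*Combined protocol and SAP*

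**What the plan says.** Section 10.4.1 (Objective #1) lists the summaries of mean counts and of time in each activity category, and then turns to the guideline: "We will then estimate the frequency of children who met Canadian physical activity recommendations on any day, and the average number of days". The days meant are those that satisfied the guideline, and the criteria are given as "180 minutes of activity classified as LPA or MVPA, working towards 60 minutes of activity classified as MVPA". The paragraph that follows reads "The above analyses will be repeated using data restricted to indoor wear time, in and around the household wear time"; it then names weekday and weekend data as well. It excludes none of the preceding analyses, and attainment is the one directly above it.

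Section 10.1 makes both criteria absolute daily totals. For total activity, the quantity derived per child is the "proportion of days on which each child reached or exceeded 180 minutes of activity classified as LPA or MVPA". For MVPA alone, section 10.1 adds a second quantity of the same kind: "the proportion of days on which each child reached or exceeded 60 minutes of activity classified as MVPA". It also defines indoor wear time and wear time in or around the home as parts of the child's eligible wear time.

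The list of location-restricted measures in section 10.1 covers mean counts per 15 seconds, average daily minutes, and the proportion of time in each category. Attainment is not in that list, but nothing there withdraws it from the general instruction in 10.4.1. The documents do not rescale the thresholds to time in the location and give no caution on interpretation.

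**The concern.** A whole-day target is to be judged on part of the day. Active minutes accrued elsewhere are dropped while the 180- and 60-minute thresholds stay fixed. A child who meets the guideline over the day can then be reported as not meeting it indoors or at home, with no difference in how active the child is there.

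A reader shown whole-day and indoor attainment side by side would naturally take the lower indoor figure to mean that children are less active indoors. The figure mixes two things: how active the child is in the location and how long the child is there. The plan also intends to compare attainment with published results from similar populations. A part-day figure is not comparable with a whole-day one.

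**Working it through.** **The plan's own figures.** The documents give no attainment estimate to reproduce. The only computed design figure, the ±2.45 margin in section 9.6, reproduces (1.96 × 9.7 / √60 = 2.454) and has no bearing on this point.

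**Step 1: direction, without assumptions.** Let A be active minutes over the whole eligible day and A_loc those accrued in the location. Location time is a subset of the day, so A_loc ≤ A. Whenever A_loc ≥ 180, A ≥ 180 as well. On the same valid days, restricted attainment is therefore at most whole-day attainment. The two are equal only if no day needs minutes from elsewhere to reach the target. The same holds for 60 minutes of MVPA.

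**Step 2: how far the bar rises.** Let f be the share of eligible wear spent in the location, with equal activity intensity everywhere. Reaching 180 minutes there requires 180/f minutes over the whole day: 200 at f = 0.9, 225 at f = 0.8 and 257 at f = 0.7. At 600 minutes of wear, the share of location time that must be active is 180/(600f): 30% for the whole day, 33.3% at f = 0.9, 37.5% at f = 0.8 and 42.9% at f = 0.7.

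**Step 3: illustrative size.** The documents give neither f nor a distribution of daily active minutes. Both are assumed here. With daily active minutes normal with mean μ and SD σ, the chance of meeting threshold T in the location on a given day is P(Z ≥ (T/f − μ)/σ). For T = 180, μ = 240, σ = 50 and f = 0.9, this is P(Z ≥ (200 − 240)/50) = P(Z ≥ −0.8) = 79%.

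| Assumed daily minutes | Target | Whole day | f = 0.9 | f = 0.8 | f = 0.7 |
|---|---|---|---|---|---|
| 240 (SD 50) active | 180 | 88% | 79% | 62% | 37% |
| 300 (SD 60) active | 180 | 98% | 95% | 89% | 76% |
| 70 (SD 25) MVPA | 60 | 66% | 55% | 42% | 27% |

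A check on a different footing assumes 600 minutes of wear and a daily active share with mean 35% and SD 8 points. Attainment of 180 minutes is then 73% for the whole day, 58% at f = 0.9 and 38% at f = 0.8. Intensity is the same in every column, so each fall comes only from counting fewer minutes.

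**Step 4: the two planned summaries.** The expected number of days met is the number of days times the daily chance, so it falls in proportion. Over 7 days in the first row it is 7 × 0.885 = 6.2, then 5.5, 4.3 and 2.6. Any-day attainment is 1 − (1 − p)^d for d independent days (an assumption; correlation between a child's days would lower it). Over 7 days it is 99.9% at f = 0.8 and 96% at f = 0.7. With the minimum of 3 valid days that section 10.1 allows, it is 94% at f = 0.8 and 74.5% at f = 0.7.

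**Step 5: weekday and weekend repeats.** These keep whole days, so the daily criteria remain valid. The two summaries nevertheless depend on how many days are counted. With a 40% daily chance and independent days, any-day attainment is 1 − 0.6^7 = 97% over 7 days, 1 − 0.6^5 = 92% over 5 and 1 − 0.6^2 = 64% over 2.

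**The case against.** The best defence is that section 10.1 already specifies the location outcomes, and attainment is not among them. On that view only one over-broad sentence is at fault. This largely stands, and it is why the repair is small; but 10.4.1 as written still orders the repeat, and silence in 10.1 does not cancel it.

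Restricted attainment can also be given a valid literal meaning: whether the guideline amount was accrued in that location alone. The plan never poses that question, so the result would need its own label and caution.

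The fall may be modest. Section 6.1 expects these children to spend their days at home, and section 10.1 counts rooftops, common areas, private courtyards and neighbouring apartments as around the home. A high f is therefore plausible, at least for the home repeat. At f = 0.9 the falls are 88% to 79%, 98% to 95% and 66% to 55%, and any-day attainment moves much less. This stands as a limit on size, not on direction.

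Two stronger readings are tempting and are not supported:

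- A reader might infer that the valid-day rule is also at fault, because applying it to indoor minutes would leave only days spent mostly indoors. Section 10.1 says "A given day will be considered eligible for inclusion if there are at least 10 hours/day (600 min" of wear within the child's waking period, or within 8am to 8pm when those times are missing. That is whole-day wear, not location wear, and the rule needs no change.
- A reader might infer that the artefact would favour the hypothesis that the home environment limits activity. Objective 2 tests that hypothesis with mixed models on mean counts, not with attainment. The artefact also bears hardest on children who go out most and hardly touches those who stay at home, so between children it does not favour the hypothesis.

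**Conclusion.** The point holds for guideline attainment in the indoor and in/around-home repeats. The direction follows from the definitions alone. The size is illustrative: it rests on assumed distributions, equal intensity in all locations and a value of f that the documents do not supply. Under 240 (SD 50) active minutes, daily attainment of 180 minutes goes from 88% to 79%, 62% and 37% as f goes from 1 to 0.9, 0.8 and 0.7. The number of days met falls in proportion, and any-day attainment falls much less.

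Only a descriptive repeat is affected. Mean counts per 15 seconds, proportions of wear time, whole-day attainment and the Objective 2 and 3 models are untouched. It would be wrong to infer that the primary outcome or the main attainment result is compromised. Severity is minor to moderate.

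**What to change.** In section 10.4.1, Objective #1:

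1. State that guideline attainment is computed only on whole eligible days: all days, weekdays and weekends.
2. For weekdays and weekends, report the proportion of valid days meeting each criterion. Section 10.1 already derives this proportion per child. Do not compare any-day attainment or the number of days met between subsets with different numbers of days.
3. For the indoor and in/around-home repeats, drop attainment. Report LPA plus MVPA, and MVPA alone, as a percentage of wear in that location or as minutes per hour of it, next to the minutes of wear there. This agrees with the measures already listed in section 10.1.

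Leave the 600-minute day rule as it is. The cost is a change of wording; no new data are needed, and the percentages and wear minutes are already planned.
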